## 7 Research Design and Methods

## 7.1 Study Design

This study has two overall arms with different study designs and distinct patient populations.

### 7.1.1 Study design for Aims 1 and 2

This study will perform a retrospective electronic health record-driven study of three institutions in the STAR Clinical Research Network.

Aims 1 and 2 will be addressed by a retrospective cohort study design that does not involve enrolling patients. We will analyze patient-level and provider-level data from electronic health records (EHRs) from STAR Clinical Research Network (CRN) institutions that have been mapped to the Common Data Model (CDM). These institutions include Duke University Health System, Vanderbilt University Medical Center, Medical University of South Carolina, and Wake Forest University Health Sciences.

## 7.1.2 Study design for Aim 3

Aim 3 will be addressed by a prospective, qualitative descriptive study enrolling consented participants—patients and health care providers—across four sites to identify the contextual, patient and healthcare provider-reported barriers and facilitators for achieving optimal primary CVD prevention. This aim provides the qualitative framework to develop a contextually appropriate model to prevent CVD among URM PLWH.

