## 12 Data analysis & statistical considerations

#### 12.1 Analysis Plan for Aim 1

For this aim, the primary outcome variable is referral to a cardiology specialist within 6 months of baseline. This will be measured as a binary variable, with 'yes' defined if there is documented evidence that a referral is made within 6 months of becoming eligible by CVD risk score and kept within 3 months of referral, and 'no' otherwise. We will also determine the time from baseline to cardiology referral and the time until the first visit with the cardiology specialist.

We will consider a number of patient and provider factors evaluated at baseline that are potentially associated with referral to a cardiology specialist. Patient factors will include demographic factors (age, sex, race, ethnicity), level of ASCVD risk, Charlson comorbidity index, SES (e.g.; 5 digit zip code, health insurance ([yes/no]), type of health insurance (Medicare, Medicaid, private, Ryan White, etc.), and history of keeping appointments during 2 years prior to baseline. Provider factors will include primary management strategy (coprimary management defined as having both an HIV doctor and Primary Care Practitioner vs. HIV provider as primary care), and years of practice since training. Cardiologist availability will be a site-determined variable. Based on prior literature, we are specifically considering sex as a biological variable that may be related to specialty referral. 

Baseline characteristics of the cohort will be summarized overall and by referral status. We will include the patient and provider factors described above, as well as vital signs (including weight, body mass index and blood pressure), laboratory measures (particularly total and HDL cholesterol, CD4 cell count, HIV viral load), and relevant medications (ART and cardiovascular medications). We will document the patterns of HIV related CVD comorbidity in the study population, as the funding opportunity announcement specified.

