Univariable and multivariable logistic regression analysis will be used to identify factors that are most strongly associated with cardiology referral. The patient and provider factors listed above are of primary interest and will be included as covariates in the regression models. Subgroups of primary interest will be defined by race/ethnicity (e.g., Non-Hispanic Black, Hispanic Black, Other) and by Insurance Status (None, Medicare, Medicaid, private, Ryan White, etc.). Univariable and multivariable associations will be reported stratified by sub-groups, and reported with interaction tests between the subgroup and other factors. Statistical significance will be determined at the two-sided 0.05 level.

We will also consider a number of sensitivity analyses to evaluate robustness of our study results to various assumptions. For example, to evaluate the impact of drop-outs we will re-run analyses only including patients with routine follow-up within the health care system (e.g., as evidenced by a certain number of visits during the study period). In another sensitivity analysis, we will extend the period for counting a cardiologist referral from 6months to 12 months. If there are subgroups of patients where referral is extremely common (e.g., very high ASCVD risk) or extremely uncommon (e.g., uninsured patients) then we will evaluate the effect of excluding these subgroups in additional sensitivity analyses.

## 12.1.1 Expected power and sample size for Aim 1

Aim 1 expected power and sample size: Preliminary counts collected from sites suggest that we will identify at least 6,000 adult PLWH of Black/African-American and other URM race/ethnicity. We anticipate that 20-25% of these patients will meet the ASCVD risk threshold and be eligible for inclusion in the population for Aim 1, for an anticipated sample size of 1,200-1,500 patients. Preliminary data from our EHR and clinical experience suggests that 20-25% of those at elevated risk will have been referred to a cardiologist. This would provide at least 80% power to detect an association between cardiology referral, and a binary risk factor with 0.33 incidence, when the odds ratio for the association is 1.6 or greater. With 1,500 eligible patients the power to detect an association with an odds ratio of 1.5 would be >85%.

#### 12. 2 Analysis Plan for Aim 2

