Starting with the population selected for Aim 1, we will create a sub-population by matching patients referred to a cardiology specialist (the primary outcome variable for Aim 1) to similar non-referred patients. The goal of this matching is to balance factors that may be confounders of the relationship between referral and cardiovascular outcomes. We will identify factors found to be associated with cardiology referral from Aim 1, as well as factors that are expected to be associated with outcomes such as, age, race, insurance status/type, ASCVD risk score, and comorbidity index. We will not seek to match on factors that may be associated with referral but unlikely to be directly associated with outcomes. For example, we may not want to match on cardiologist availability by site if this is only related to referral and not independently to outcomes. Variables that potentially modify the effect of referral (e.g., sex, race/ethnicity, insurance status) will be included among the matching factors. Patients will be matched within sites and year of baseline encounter.

For each patient referred to a cardiologist we will identify one non-referred patient (1:1 matching) within each site. We will match using values of the individual confounders, with an exact match on sex, race/ethnicity, insurance status/type, and to within a small caliper for continuous variables (e.g., ±5 years for age). Matched pairs will be identified using optimal matching. If this approach fails to identify an adequate number of matched pairs, then 1:1 matching will be implemented using a propensity score.

Once the matching has been implemented, the same baseline characteristics reported for Aim 1 will be summarized in the matched cohort by referral status. Metrics (e.g., standardized differences) will be reported to evaluate how well-balanced the referred and non-referred groups.

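### Aim 1 tests years of practice, which is nearly constant across a provider's patients, with no allowance for shared providers; if their referrals are correlated, its type I error exceeds 5%

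*Combined protocol and SAP*

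**What the plan says.** Hypothesis 1 (section 4) holds that patient-level and provider-level factors are both associated with cardiology referral. Section 12.1 names two provider factors: the primary management strategy and "years of practice since training". Of all the listed factors it says: "The patient and provider factors listed above are of primary interest and will be included as covariates in the regression models". The method is given in one sentence: "Univariable and multivariable logistic regression analysis will be used to identify factors that are most strongly associated with cardiology referral". The test level follows: "Statistical significance will be determined at the two-sided 0.05 level".

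No section gives Aim 1 a provider random effect, generalised estimating equations (GEE) or a cluster-robust variance. The sensitivity analyses in 12.1 deal with drop-out, a longer referral window, and subgroups in which referral is very common or very rare. The only variance allowance for correlation is in section 12.2, where the Aim 2 Cox models use a sandwich estimate for the matched pairs.

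Section 12.1.1 claims at least 80% power for an odds ratio of 1.6 with 1,200 to 1,500 patients, and more than 85% for an odds ratio of 1.5 with 1,500 patients. Both figures are for a binary factor present in 0.33 of patients, with 20-25% referred.

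**The concern.** The outcome requires that a referral be made, which is partly the provider's decision. Some providers may refer more readily than others for reasons that the covariates do not capture. Their patients' outcomes would then be correlated.

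Ordinary logistic regression counts every patient as independent information. That matters most for a covariate that is the same, or nearly so, for all of a provider's patients. The information about years of practice comes mainly from comparing providers, so its effective sample size can be well below 1,200-1,500. The model-based standard error ignores this. A p-value below 0.05 for years of practice would then be weaker evidence than it appears, for a factor that the plan places among those of primary interest.

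**Working it through.** **Step 1: reproduce the stated power.** Inputs from 12.1.1: N = 1,200 or 1,500, referral 20% or 25%, factor prevalence 0.33, odds ratio 1.6 or 1.5, two-sided 0.05. I solved for the referral rates without (p0) and with (p1) the factor so that 0.67·p0 + 0.33·p1 equals the overall rate, then applied the pooled two-proportion formula for independent patients.

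For N = 1,200, 20% referred and odds ratio 1.6:
- p0 = 0.174 and p1 = 0.252, a difference of 0.078, with 804 and 396 patients.
- The standard error is 0.0246 under the null and 0.0256 under the alternative.
- Power = Φ((0.0782 − 1.96 × 0.0246)/0.0256) = 88.0%.

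| N | Referred | Odds ratio | Power |
|---|---|---|---|
| 1,200 | 20% | 1.6 | 88.0% |
| 1,200 | 25% | 1.6 | 92.1% |
| 1,500 | 20% | 1.6 | 93.7% |
| 1,500 | 25% | 1.6 | 96.4% |
| 1,500 | 20% | 1.5 | 85.5% |
| 1,500 | 25% | 1.5 | 90.2% |

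The plan's figures are met with no design effect, so they match a calculation for independent patients.

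**Step 2: type I error for a provider-constant factor.** The number of patients per provider (m) and the residual ICC of referral on the probability scale are assumptions.

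Design effect DE = 1 + (m − 1) × ICC. The correct interval is √DE times as wide as the model-based one. Actual type I error = 2 × (1 − Φ(1.96/√DE)).

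| m | ICC | DE | √DE | Type I error |
|---|---|---|---|---|
| 10 | 0.01 | 1.09 | 1.04 | 6.0% |
| 20 | 0.02 | 1.38 | 1.17 | 9.5% |
| 20 | 0.05 | 1.95 | 1.40 | 16.0% |

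**Step 3: does the factor have to be exactly constant?** Years of practice is taken at each patient's baseline, so it drifts within a provider over calendar time. Let ρx be the within-provider correlation of the covariate, so that DE = 1 + (m − 1) × ICC × ρx. With an assumed ρx of 0.92, m = 20 and ICC 0.05, DE = 1 + 19 × 0.05 × 0.92 = 1.87 and the type I error is 15.2%. Drift makes little difference.

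**Step 4: simulation.** Ordinary logistic regression with site terms and a continuous, drifting years-of-practice variable that has no true effect rejected in:
- 5.2-6.3% of runs (m = 10, ICC 0.01);
- 9.3-10.1% (m = 20, ICC 0.02);
- 15.5-16.2% (m = 20, ICC 0.05);
- 20.5% with unequal panels averaging 20 patients and ICC 0.05.

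Without site terms, the rates were 6.9% (m = 10, ICC 0.01) and 14.9% (m = 20, ICC 0.05). With no provider correlation, a separate simulation of a provider-constant factor stayed at 4.5-5.8%.

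**Step 5: patient-level factors.** A simulated patient factor rejected in 4.1-5.6% of runs. A patient factor that itself clusters by provider, as insurance type might, is not fully protected. With m = 20, ICC 0.05 and an assumed ρx of 0.1 to 0.3, DE is 1.095 to 1.285 and the type I error is 6.1% to 8.4%.

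**The case against.** The strongest reply is that the size is chosen, not derived. The documents give no number of providers, no panel sizes and no ICC, and at the low end the test is close to nominal. The ICC scale matters too. An ICC of 0.05 on the latent logistic scale is about 0.028 on the probability scale at 20% referral. With m = 20 this gives 11.3% by formula; simulation on the latent scale gave 11.5% with equal panels and 17.4% with unequal ones. The outcome also requires the appointment to be kept, which depends partly on the patient and may weaken provider correlation. All of this stands as a limit on size. It does not change the direction.

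The list of sensitivity analyses is introduced as examples, so a clustered analysis is not ruled out. But none is named, and the primary test would still be the ordinary model.

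A reader might infer that the claimed power is wrong. The documents do not support that: the figures reproduce, and they are for an unspecified binary factor. A calculation for a provider-constant binary factor would give lower power (62% for odds ratio 1.6 at N = 1,200, 20% referred and DE 1.95), but the plan lists no such factor: management strategy can differ among one provider's patients, and years of practice is not described as binary.

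A reader might also take the 2012-2016 accrual period as a limit of 4 years' drift. Those dates are in the Aim 2 sample size section (12.2.1), and section 8.1 allows dates to be adjusted. The conclusion does not need that limit.

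**Conclusion.** The point holds in conditional form. The planned Aim 1 model protects the 5% level for years of practice only if referral is uncorrelated among a provider's patients after adjustment. If the correlation is positive, the interval is too narrow. Under the assumed probability-scale ICCs and equal panels, the type I error runs from about 6% to 16%, and it is higher with unequal panels. No single value in that range should be presented as the expected one.

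Two wider readings are not supported. The Aim 1 results as a whole are not undermined, because patient-level factors are much less affected. Nor does the point extend to cardiologist availability. The plan says "Cardiologist availability will be a site-determined variable" but does not make clear that it is a tested covariate; whether it could be told apart from other site differences is a separate question from provider clustering.

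**What to change.** In section 12.1:
- State a rule that attributes each patient to one provider at the index encounter, including patients managed by both an HIV doctor and a primary care practitioner.
- Report the Aim 1 logistic models with provider-clustered sandwich variance (GEE with independence working correlation). For the same covariates the odds ratios are those of the planned models; only the standard errors change.
- Name a small-cluster correction. In simulation the uncorrected sandwich test still rejected in about 6-12% of runs with 40-60 providers. The simple G/(G − 1) correction gave 5.1-6.8%, where G is the number of providers, and a Mancl-DeRouen correction gave 3.6-5.0%.

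In section 12.1.1, say that the power figures assume independent patients and so apply to patient-level factors.

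Site fixed effects are a separate choice: they would change the adjustment set, and hence the odds ratio being estimated.

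The cost is small. No extra patients are needed, and giving a patient a value for years of practice already requires a link to a provider. Section 8.2 mentions NPI only as an example of a data source, so the link should be confirmed through the feasibility survey in 8.1.1. The statistical price is a wider interval for years of practice.

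### Aim 1 pools four health systems, but its logistic models have no site or index-year term, so an odds ratio can mix within-site and between-site association

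*Combined protocol and SAP*

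**What the plan says.** Section 12.1 plans univariable and multivariable logistic regression for referral and fixes the covariates: "The patient and provider factors listed above are of primary interest and will be included as covariates in the regression models". The list covers age, sex, race, ethnicity, ASCVD risk, Charlson index, socioeconomic measures (zip code and insurance are the examples), appointment history, management strategy and provider years of practice. Site and index year are absent. No stratification by site, random effect or cluster-robust variance is stated, and none of the named sensitivity analyses concerns site or year.

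One site-related item follows the provider factors in a sentence of its own: "Cardiologist availability will be a site-determined variable". Its coding is not given.

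Sections 7.1.1 and 7.2.1 name four health systems, and section 8.2 merges their data into one database. Section 12.2.1 gives accrual as 2012-2016. For Aim 2, section 12.2 says: "Patients will be matched within sites and year of baseline encounter".

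**The concern.** Aim 2 treats site and year as things to hold constant. Aim 1, where referral is itself the outcome, does not. Health systems may differ in how often they refer and in how a referral made and kept is documented. They may also differ in insurance mix, race/ethnicity mix and co-management, which are factors or subgroups of primary interest. If both kinds of difference are present, a pooled odds ratio for insurance, say, partly reflects which system the patient attends. The Aim 1 question is which patient and provider factors go with referral, so a between-system contrast could be reported as a patient-level determinant.

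**Working it through.** **1. The plan's own power figures.** Inputs from sections 12.1 and 12.1.1: "Statistical significance will be determined at the two-sided 0.05 level"; "for an anticipated sample size of 1,200-1,500 patients"; "20-25% of those at elevated risk will have been referred to a cardiologist"; "a binary risk factor with 0.33 incidence, when the odds ratio for the association is 1.6 or greater". The plan claims at least 80% power for odds ratio 1.6, and over 85% for 1.5 with 1,500 patients.

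Solve 0.67·p0 + 0.33·p1 = overall referral rate at the given odds ratio. Then power = Φ[(p1 − p0 − 1.96·SE0)/SE1], with SE0 pooled and SE1 unpooled.
- N = 1,200, 20% referral, odds ratio 1.6: p0 = 0.1742, p1 = 0.2524, SE0 = 0.02456, SE1 = 0.0256. Power = Φ(1.17) = 88.0%.
- N = 1,500, 20% referral, odds ratio 1.5: p0 = 0.1778, p1 = 0.2450, SE0 = 0.02196, SE1 = 0.02279. Power = Φ(1.06) = 85.5%.

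Both claims reproduce. The issue is model specification, not power.

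**2. Pooled odds ratio when the within-site odds ratio is 1.** The site rates are assumptions. Take four equal sites with referral r and factor prevalence x, independent within site. The pooled cells are a = mean(r·x), b = mean(x) − a, c = mean(r) − a, d = 1 − a − b − c, and the odds ratio is ad/(bc). With SE = √[(1/a + 1/b + 1/c + 1/d)/N] and z = ln(OR)/SE, the rejection rate is Φ(z − 1.96) + Φ(−z − 1.96).

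Fully aligned case, r = 12/18/26/34% and x = 20/28/38/48%:
- a = (0.0240 + 0.0504 + 0.0988 + 0.1632)/4 = 0.0841; b = 0.335 − 0.0841 = 0.2509; c = 0.225 − 0.0841 = 0.1409; d = 0.5241.
- Odds ratio = (0.0841 × 0.5241)/(0.2509 × 0.1409) = 1.25; ln = 0.2206.
- N = 1,200: SE 0.1440, z 1.53, rejection 33%. N = 1,500: SE 0.1288, z 1.71, rejection 40%.

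| Assumed referral by site | Assumed prevalence by site | Pooled OR | Rejection |
|---|---|---|---|
| 19/21/24/26% | 27/31/35/39% | 1.03 | about 6% |
| 15/20/25/30% | 25/30/36/42% | 1.10 | about 10% |
| 12/18/26/34% | 20/28/38/48% | 1.25 | 33-40% |

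**3. Dependence on alignment.** Reverse the prevalences in the last row: a = (0.0576 + 0.0684 + 0.0728 + 0.0680)/4 = 0.0667, and the odds ratio is (0.0667 × 0.5067)/(0.2683 × 0.1583) = 0.80. Over all 24 assignments of those prevalences to sites, the geometric-mean odds ratio is 1.00. Rejection at N = 1,200 averages 14%, with median 10%.

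**4. If an availability term is in the model** (last row, N = 1,200). A 1-4 score in the order of site referral gives odds ratio 1.00 and 5% rejection. A high/low split in that order gives 1.04 and 6%. Averaged over all 24 orderings of the score, rejection is 20%.

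**5. Cost of adjustment.** Replace N by N(1 − R²), where R² is the assumed share of the factor's variance explained by site and year.

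| Case | No adjustment | R² 0.05 | 0.10 | 0.20 |
|---|---|---|---|---|
| N 1,200, 20% referral, OR 1.6 | 88% | 86% | 85% | 80% |
| N 1,500, 20% referral, OR 1.5 | 85.5% | 84% | 82% | 77% |
| N 1,500, 25% referral, OR 1.5 | 90% | 89% | 87% | 83% |

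**The case against.** The strongest reply is that 33-40% is not a prediction. It needs an unadjusted model and site referral and prevalence in the same rank order; steps 3 and 4 show how far it falls otherwise. That stands. A wider assumed spread (referral 10-35%, prevalence 13-53%) would give an odds ratio of 1.43, close to the effects the study is powered for. Nothing in the documents supports so wide a spread.

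A reader might also infer that the plan tests a site-level factor on four sites. Section 12.1 puts availability in neither factor list and leaves its coding open, and site-determined could mean reported by the site. Section 12.2 does speak of availability by site, which favours the site-level reading. Entered as a four-level class variable it would be equivalent to site, and the site confounding would disappear. Only as a single-degree-of-freedom term would it be anticonservative. In simulation with four sites of 300, a null two-level term rejects in 11%, 26% and 41% of studies at assumed between-site SDs of 0.1, 0.2 and 0.3 on the logit scale.

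A third tempting inference is that the error passes into Aim 2. It does not hold, because Aim 2 matches within site and year and chooses several matching factors for their expected relation to outcome.

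For index year no size can be given. The window comes from the Aim 2 power paragraph, and section 8.1 allows dates to change. Year rests on the contrast with Aim 2 and on its low cost. Zip code may absorb some site difference, but it does not replace a site term.

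**Conclusion.** The point holds as a specification gap. As written, the Aim 1 models leave site and index year unadjusted, and site differences can bias the odds ratios in either direction. Under the assumed rates the unadjusted effect runs from negligible (1.03) to 1.25, with 14% rejection on average over alignments of the widest tabulated case. All of this rests on assumed site rates, four equal sites and no within-site association. The plan's power statements are sound, and Aim 2 is not affected by this route. The site count also needs reconciling: section 7.1.1 says three and names four, and section 8.1 names three. This should be changed before analysis because prevention is cheap, not because serious bias has been shown.

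**What to change.** In section 12.1, add site (fixed effect, one level per health system) and index year (categorical, or linear where data are sparse) to the multivariable and interaction models. In small subgroup models, keep site and use a simpler year term, or take subgroup effects from the interaction model. Five equal insurance groups would have only 240/5 = 48 to 375/5 = 75 referrals each.

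State how availability is defined. If it is constant within site, it is aliased with the site effect, so report it and referral rates by site descriptively, without a patient-level p-value. If it can be defined below site level or varies over time, it may stay in the model alongside site.

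Cost: 4 − 1 = 3 degrees of freedom for site and up to 5 − 1 = 4 for year, against 1,200 × 0.20 = 240 to 1,500 × 0.25 = 375 referrals. Some power is lost: at 1,500 patients and 20% referral, power for odds ratio 1.5 would fall slightly below the stated 85%. There would be no availability p-value if it is site-constant.

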Then, DCRI will take the query data that the sites provide to identify and further stratify data for potential cohort of patients, based on additional clinical characteristics. At the earliest clinical contact within look back period, we will identify HIV status according to ICD9/10 codes and prescription of ART. We will include individuals >18 years of age and < 99 years of age, plus will ascertain time-updated data for the following potential characteristics:

hemoglobin, creatinine (or glomerular filtration rate), age, sex, race, ethnicity, insurance status, total cholesterol, HDL cholesterol, LDL cholesterol, systolic blood pressure, prescription of anti-hypertensive medications, family history of coronary artery disease, presence of diabetes, previous diagnosis of any acute myocardial infarction, hospitalization for heart failure, acute coronary syndromes, stable or unstable angina, arterial revascularization, stroke, transient ischemic attack and peripheral arterial disease presumed to be of atherosclerotic origin determined by ICD9/10 codes. Behavioral factors are smoking status, number of clinic visits per year, length of time between clinic visits and missed appointments with specialist after referral. Data will also be ascertained on HIV viral load, CD4 count, prescription of any ART and length of time on all medications. This list captures the majority of the data related to our scientific aims and will be modified as the availability of these data are discovered.

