For this aim, the primary outcome variable will be blood pressure control based on prevailing guidelines during the study period (blood pressure <140/90 mmHg). The co-primary outcome is lipid control, defined by prevailing guidelines during the study period. These outcomes will be evaluated longitudinally during 5-years of follow-up. Secondary outcome variables include time to the first major adverse cardiovascular event (MACE = cardiovascular death, myocardial infarction (MI)), stroke, heart failure hospitalization, peripheral artery disease procedure, coronary artery disease (based on diagnosis codes or coronary artery revascularization procedure), and all-cause death. Events ascertained from relevant diagnosis and procedure codes, and from a query of the National Death Index Plus, State Death records, Social Security Death Masterfile, Hospital death record and/or similar death record for causes of death including cardiovascular

death. We will also evaluate time to BP control and time to lipid control among patients who were not controlled at study start. For this Aim, "time zero" for the matched patient pair will be defined as the time from baseline (see Aim 1) when the referred patient kept their cardiology appointment. Events will be ascertained starting from time zero and until the end of follow-up. For each patient, end of follow-up will be defined as the date of the last outcome event or health system encounter without an event, occurring ≥3 months prior to the retrospective study review period of December 31, 2020 of the EHR.

To evaluate the association between cardiology referral and subsequent blood pressure and lipid control (coprimary outcomes), we will first evaluate these measures between referred and non-referred patients at baseline, and then compare prevalence and time trends between referred and non-referred patients using methods appropriate for longitudinal data analysis. For example, we will explore whether the proportion of patients with adequately controlled BP at each year is higher in referred compared to non-referred patients. Because these analyses are conducted in the matched population, the results are adjusted for the potential confounders included in the identification of the matched pairs.

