To evaluate the association between cardiology referral and CVD events (secondary outcomes), the cumulative incidence of primary and secondary outcomes will be summarized in the referred and matched non-referred patients. Follow-up will be censored at the earliest of 8 years or end of follow-up. For each outcome variable a Cox regression model will be fit, and the hazard ratio (referral vs. not referred) and 95% CI, and p-value will be reported. The Cox regression analysis will account for the matched pairs design using the empirical sandwich variance estimate. Statistical significance will be determined at the two-sided 0.05 level.

The relationship between referral status and outcomes will also be evaluated within subgroups of primary interest: sex, race, ethnicity and insurance as defined in Aim 1. Evidence for a differential association between referral status and CVD outcomes for different subgroups will be quantified using an interaction test in the Cox regression analysis. The considerations and approaches outlined in Aim 1 regarding missing data and sensitivity analyses will also be applicable for Aim 2.

#### 12.2.1 Expected power and sample size for Aim 2

Aim 2 expected power and sample size: With an anticipated cardiology referral rate of 20-25% among 1,200-1,500 patients included in Aim 1, the sample size in the matched cohort study is expected to be 250-375 per group. These patients will be accrued into the study over 5 years (2012-2016) and then followed to evaluate BP and lipid control, and for cardiovascular events for up to 8 years through December 31, 2020. For the primary endpoints, the rates in the non-referred group are anticipated to be 30% and 45% for BP and lipid control, respectively. With 300 per group, the study is predicted to have >70% power to detect a 10% increase in rate of BP control, and >95% power to detect a 15% increase in rate of lipid control due to cardiology referral. For the secondary endpoints, the rate of MACE events is anticipated to be fairly low (i.e., a cumulative incidence ~5% at 5 years and ~10% at 10 years) and we anticipate modest power to detect even large reductions in risk of CVD events due to cardiology referral. However, this aim will provide useful information about clinical event rates and estimates of the potential to effect event rates that could be attributed to cardiology referral.

#### 12. 3 Analysis Plan for Aim 3

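### The 20-25% planning rate is not shown to count the timely, kept referrals that define the Aim 1 outcome and Aim 2 exposure; the Aim 2 range should start at 240, where the quoted power does not hold

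*Combined protocol and SAP*

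**What the plan says.** **Planning rate.** Section 12.1.1 expects that "20-25% of those at elevated risk will have been referred to a cardiologist", citing preliminary EHR data and clinical experience, "for an anticipated sample size of 1,200-1,500 patients". It gives no period over which referral is counted and does not say whether the visit took place. The power claims are at least 80% for an odds ratio of 1.6, and above 85% for an odds ratio of 1.5 with 1,500 patients. Both use a risk factor present in 0.33 of patients.

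**Outcome and exposure.** Section 12.1 scores a patient as referred only if "a referral is made within 6 months of becoming eligible by CVD risk score and kept within 3 months of referral"; everyone else is scored no. Section 12.2 builds the Aim 2 cohort by "matching patients referred to a cardiology specialist (the primary outcome variable for Aim 1) to similar non-referred patients", and starts follow-up "when the referred patient kept their cardiology appointment".

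**Aim 2 size.** Section 12.2.1 applies the same 20-25% to the same 1,200-1,500 and concludes that "the sample size in the matched cohort study is expected to be 250-375 per group". Power is then given at one size, 300 per group: above 70% for blood pressure (30% rising by 10 points) and above 95% for lipids (45% rising by 15 points).

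**The concern.** A referral that is made late, not kept, or kept late counts as a referral in ordinary usage but is scored no in Section 12.1. It also cannot supply an exposed patient in Aim 2, whose time zero is the kept visit. The plan foresees both kinds of loss. Section 8.1 collects "missed appointments with specialist after referral", Section 12.1 lists appointment-keeping history as a factor, and Section 12.1 also has a sensitivity analysis that widens the referral window to 12 months. Nowhere is the 20-25% said to be net of such losses, and nowhere is it reduced for them.

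At stake are the Aim 1 event rate, the number of matched pairs in Aim 2, and the power for the two co-primary outcomes. Separately, the Aim 2 range does not quite follow from its own inputs, and power is quoted at an interior point of that range only.

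**Working it through.** **1. Aim 2 group size, from the inputs in Sections 12.1.1 and 12.2.1.**

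- 1,200 × 0.20 = 240
- 1,200 × 0.25 = 300
- 1,500 × 0.20 = 300
- 1,500 × 0.25 = 375

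The upper end matches the plan. The lower end is 240, not 250. Both ends use the full rate, with every referral qualifying and every referred patient matched.

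**2. Reproducing Aim 2 power.** For two independent proportions, two-sided 0.05, n per group:

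power = Φ{[|p1 − p0| − 1.96 √(2p̄(1 − p̄)/n)] / √([p0(1 − p0) + p1(1 − p1)]/n)}, with p̄ the mean of p0 and p1.

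Blood pressure, 0.30 v 0.40, n = 300: p̄ = 0.35, null SE = √(0.455/300) = 0.03894, alternative SE = √(0.45/300) = 0.03873. Then (0.10 − 1.96 × 0.03894)/0.03873 = 0.611, power 72.9% (stated >70%).

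Lipids, 0.45 v 0.60, n = 300: p̄ = 0.525, null SE = √(0.49875/300) = 0.04077, alternative SE = √(0.4875/300) = 0.04031. Then (0.15 − 1.96 × 0.04077)/0.04031 = 1.739, power 95.9% (stated >95%).

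Both stated figures reproduce at 300.

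**3. The same formula across the range, assuming no loss.**

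| n per group | Blood pressure | Lipids |
|---|---|---|
| 240 (correct lower end) | 63.3% | 91.1% |
| 250 (stated lower end) | 65.0% | 92.1% |
| 300 | 72.9% | 95.9% |
| 375 | 82.0% | 98.5% |

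Neither quoted power holds at the lower end, whether that is 240 or 250.

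**4. Margin at 300 if some referrals do not qualify.**

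- 7% loss: 300 × 0.93 = 279, blood pressure power 69.8%.
- 5% loss: 300 × 0.95 = 285, lipid power 94.995%, just under 95%.

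**5. Aim 1.** With marginal event rate r and exposure 0.33, solve 0.67·p0 + 0.33·p1 = r with p1 = OR·p0/(1 − p0 + OR·p0). Then apply the two-proportion formula with a 33/67 split, which replaces p̄ by r and uses the two group sizes.

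- N = 1,200, OR 1.6, r = 0.20: p0 = 0.174, p1 = 0.252, power 88.0%. At r = 0.25, 92.1%. Stated: at least 80%.
- N = 1,500, OR 1.5, r = 0.20: p0 = 0.178, p1 = 0.245, power 85.5% (86.1% by a Wald test on the log odds ratio, 84.0% by the Hsieh approximation). At r = 0.25, 90.2%. Stated: >85%.

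Effect of loss, using the two-proportion formula:

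- OR 1.6 at a 20% rate: 27% loss gives r = 0.20 × 0.73 = 0.146 and power 79.6%. The claim therefore holds to roughly that point. At a 25% rate it holds to about 41% loss.
- OR 1.5 at a 20% rate: 10% loss gives r = 0.18 and power 82.8%, so the 0.5-point margin over 85% is gone after about 2% loss (up to about 5% by the Wald form). At a 25% rate it holds to about 22% loss.

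**The case against.** The protocol uses referral loosely. Section 4 names the same Aim 1 outcome as a visit with a cardiologist, and Section 12.2 calls the composite simply being referred. The 20-25% may therefore already be a kept-visit rate. This stands as far as it goes: a reader might infer that the stated sizes assume no missed appointments, and the documents do not establish that. They also do not establish the reverse, and even a visit rate would still lack the 6-month and 3-month limits.

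It is also fair that the Aim 2 powers are expressly conditional on 300 per group and are right at that size. The Aim 1 claim at an odds ratio of 1.6 tolerates considerable loss. And 250 for 240 is a small rounding, worth under 2 points of blood pressure power (65.0% v 63.3%). None of this supports quoting >70% and >95% alone when part of the plan's own range falls short of both.

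Finally, this is a retrospective cohort with data to December 31, 2020, so restating a planning rate adds no patients. That limits the consequence to how the study's precision is described.

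**Conclusion.** The point holds as a planning input that is not tied to the defined outcome, together with an Aim 2 range and power statement that need correction.

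Two parts need no outside assumption. The lower end is 240. Power over 240-375 is 63-82% for blood pressure and 91-98.5% for lipids, on the plan's own control rates and differences and with every referral qualifying and matched. This rests on the simple two-proportion calculation that reproduces the plan's figures; pairing and repeated measurement are not modelled.

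The third part is conditional. If the 20-25% counts all referrals, the Aim 2 sizes shrink in proportion to the share that qualifies, and the margins at 300 are gone at about 5% (lipids) and 7% (blood pressure) loss. The odds ratio 1.5 claim at a 20% rate cannot absorb more than a few percent. The odds ratio 1.6 claim is safe to about 27% loss at that rate.

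A reader might go further, assume for instance that 60-80% of referrals qualify, and report large power deficits. The documents give no such fraction. Much of the apparent drop from a low corner of that kind would also come from the plan's own 240-375 range rather than from missed visits.

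**What to change.** 1. In Section 12.2.1, correct the range to 240-375 per group and give blood pressure and lipid power at 240, 300 and 375 instead of at 300 alone. State that these sizes are before matching losses.
2. In Section 12.1.1, say what the 20-25% counts: referrals or kept visits, and over what period.
3. Obtain the event rate from the preparatory query in Section 8.1.1, programmed with the exact Section 12.1 definition (made within 6 months, kept within 3).
4. If that rate is 20-25%, one sentence confirming it closes the matter. If not, restate Aim 1 power and Aim 2 size and power from it.

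The cost is one query of a kind already planned and a few revised figures. No analysis method changes. The downside is that the stated power becomes less favourable.
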